**Study treatment must be initiated within seven (7) days of enrollment.**

## 7.0 STUDY DESIGN

The study will be a single-institution, open-label, single-arm phase II study. Since the primary endpoint is survival outcome (PFS) sample size calculation is based on a single-arm survival design. We will employ early stopping rules for lack of efficacy, based on previously reported historical controls (19% PFS at 3 months) and a large database suggesting that a progression-free rate at 3 months of >40% correlates with an active drug in the second-line setting for patients with advanced sarcoma (43). Patients will be treated with twice daily dosing of axitinib alone for the first 7 days, followed by concurrent axitinib administered twice daily at 5 mg PO twice daily, plus intravenous administration of pembrolizumab every 21 days (Figure 3). Patients will be assessed every three weeks for toxicity. After the first five patients are enrolled, we will assess safety of the combination. If 2 or fewer patients exhibit DLT, we will

then proceed with inpatient titration of axitinib dosing at each cycle based on the presence or absence of predefined toxicities (Section 7.1, Table 3). Correlative studies characterizing T-cells in tumor tissue and in peripheral blood will be performed at three timepoints: 1. pre-treatment, 2. on-treatment on cycle 3 day 1, and 3. off-study. Additional exploratory imaging investigations, and assessment of circulating tumor cells are included for all patients (See Appendix F for complete description of correlative studies).

**Figure 3. Schematic diagram of the study.** The first cycle of treatment will be seven weeks, with one week of axitinib alone prior to initiation of pembrolizumab. Subsequently, six-week cycles of treatment consist of twice daily oral doses of axitinib administered continuously with intravenous (I.V.) administration of pembrolizumab on day 1 and 22. The first five evaluable patients will be considered a safety lead-in, and will not have axitinib dose escalation above 5 mg PO bid. If 2 or fewer patients in the safety lead-in develop DLT, axitinib will then be individually titrated based on toxicity beginning on cycle 2 day 1.

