## 11.0 TREATMENT DISCONTINUATION

Treatment may be discontinued for any of the following reasons:

- The patient experiences a DLT
- The patient demonstrates radiologic progression by RECIST 1.1. **(See exception below).**
- The patient withdraws consent from the study
- The patient has not received study treatment for >21 days due to a medical/surgical events or logistical reasons not related to study therapy (e.g. elective surgery, unrelated medical events, patient vacation, and/or holidays).
- The patient has completed 24 months of uninterrupted treatment with pembrolizumab or 35 administrations of study medication, whichever is later.
- The patient experiences an adverse event that in the opinion of the Investigator makes continued study treatment an unacceptable risk
- The patient becomes pregnant (also see Section 15.6 and Appendix A for Expedited Adverse Event Reporting Requirements)
- The patient requires continuous treatment with a prohibited concomitant drug(s) for which no safe alternatives can be substituted
- The patient is significantly noncompliant with the requirements of the protocol

**Exception: Patients who exhibit radiologic progression by RECIST 1.1 may remain on the study if in the opinion of the Investigator, he/she is deriving clinical benefit from study treatment, particularly if response assessment by immune-related RECIST criteria, Choi criteria, or MRI volumetrics would not require discontinuation. A follow up confirmatory scan should be scheduled in 6 weeks. For later analysis of the primary endpoint, assuming that the confirmatory scan ALSO shows RECIST progression, the initial scan will be recorded as the first date of progression.**

Should discontinuation of study therapy occur, all efforts should be made to execute/ report End-of-Treatment and Follow-up Evaluations as completely as possible and to determine/ document the reason for discontinuation (unless the patient withdraws consent for follow-up).

If a patient wishes to withdraw consent from the study, the PI must be notified. The information regarding withdrawal (i.e. subject identifiers and date of withdrawal) should be documented in the subject's record and updated within any other research database(s).

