### 13.2 On Treatment Specimen Collection

#### 13.2.1 Cycle 3, Day 1 (PRE-DOSE)

For patients who have successfully completed two cycles of axitinib/pembrolizumab therapy, the following on-treatment correlative studies will also be performed:

- 5 core biopsies (minimum of 2), 18-22 gauge in diameter and at least 1 cm in length, will be obtained. The interventional approach used to obtain the sample (ultrasound or CT guided biopsy) will be selected by the medical personnel performing the biopsy. If possible, the biopsy site should be in the same tumor initially biopsied prior to therapy.
  - One needle core biopsy will be transported in formalin to pathology for immunohistochemistry evaluation of immunologic markers. This analysis will be performed in collaboration with [name] at MD Anderson Cancer Center. Samples will be deidentified and sent to his laboratory for multiplex immunohistochemistry.
  - Unstained slides from the formalin fixed biopsies will be sent to Nanostring for RNA expression analysis using the Universal Immunooncology Expression Panel under a collaborative research agreement to identify potential biomarkers of response.
  - The remaining cores (if any) will be collected in cell culture media and transported to the [name] lab for preparation of a single cell suspension, isolation of lymphocytes, and immediate analysis by flow cytometry. For expansion patients, additional cores will be collected for RNA analysis and performance of T cell receptor sequencing and clonality assays using the Archer DX platform.
- Patients will also undergo phlebotomy for analysis of circulating mononuclear cells with banking of serum fractions for later analysis.
  - (6) 10 cc green top tubes and (1) 10 cc purple top tube will be collected for each time point. Samples will be separated using a Ficoll gradient. Mononuclear cells will be removed, washed, treated with RBC lysis process, then either stained immediately for flow cytometric analysis or frozen for later use. Aliquots of plasma will also be frozen. One tube of PBMCs will be preserved in RNA later for T cell clonality assays using the ArcherDX platform.
  - Banked PBMCs will be sent out to Simpatica Medicine for RNA expression analysis to identify potential biomarkers of response under a collaborative research agreement.

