## 14.0 MEASUREMENT OF EFFECT

### 14.1 Antitumor Effect in Solid Tumors

For the purposes of this study, patients should be re-evaluated for response every 12 weeks (84 days, ±7 days) from date of Enrollment, (while on treatment and until there is documented evidence of disease progression for those patients who come off treatment). Imaging studies should be timed to coincide with the end of the prior treatment cycle, assessing all known sites of disease using the same type(s) of scan(s) that was/were performed at baseline. Response assessments during follow-up after disease progression should follow the same frequency (every 12 weeks, ±7 days).

Response and progression will be evaluated in this study using the international criteria proposed by the revised Response Evaluation Criteria in Solid Tumors (RECIST) version 1.1 guideline(s). Changes in the largest diameter (unidimensional measurement) of the

tumor lesions and the shortest diameter in the case of malignant lymph nodes are used in the RECIST criteria.

The following general principles must be followed:

1. To assess objective response, it is necessary to estimate the overall tumor burden at baseline to which subsequent measurements will be compared. All baseline evaluations should be performed as closely as possible to the beginning of treatment and never more than four weeks before registration.
2. Measurable disease is defined by the presence of at least one measurable lesion.
3. All measurements should be recorded in metric notation by use of a ruler or calipers.
4. The same method of assessment and the same technique must be used to characterize each identified lesion at baseline and during follow-up.

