### Analysis for Exploratory Endpoints

Although a large number of factors are being tested, we will not be making adjustments for multiple testing because these analyses are exploratory and hypothesis-generating. Findings will be validated in future larger studies.

Tumor infiltrating T-cells will be quantified by immunohistochemistry using a semiquantitative scoring system as detailed in Appendix F, Section C. We will test for association of clinical benefit status (CR/PR/SD vs PD) vs. T-cell quantity using a Wilcoxon rank sum test. We will test for association with progression-free status at 3 months (progression vs. no progression) vs. T-cell quantity using Wilcoxon rank sum test.

The expression of immune markers such as PD-1, PD-L1, PD-L2, CTLA4, TIM3, and LAG3 by immunohistochemistry will be categorized as negative (0%), low (<5%), intermediate (5-50%), or high (>50%) as detailed in Appendix F, Section C. We will test for association of clinical benefit status (CR/PR/SD vs PD) and expression category using a Chi-square test. We will test for association of expression category vs. PFS using a log-rank test.

To test for the association of the absolute change of each subset (CD4+, CD8+, T-reg, CTLA4+, TIM3+, LAG3+, memory, naïve, PD-1, Ki67) by flow cytometry in blood and tumor tissue between three timepoints (Cycle 3 marker value minus Baseline marker value, Progression marker value minus Cycle 3 marker value, Progression marker value minus Baseline marker value) with clinical benefit status (CR/PR/SD vs. PD), we will use a Wilcoxon rank sum test. Absolute changes across timepoints will be graphically presented for each marker using boxplots.

To test for the association of the absolute change between three timepoints (Cycle 3 marker value minus Baseline marker value, Progression marker value minus Cycle 3 marker value, Progression marker value minus Baseline marker value) of each subset (CD4+, CD8+, T-reg, CTLA4+, TIM3+, LAG3+, memory, naïve, PD-1, Ki67) with progression-free status at 3 months (progression vs. no progression), we will use a Wilcoxon rank sum test.

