#### **16.4 Patient Enrollment and Sample Size**

The study will be conducted at Sylvester Comprehensive Cancer Center. Our expectation is that proposed treatment will improve PFS at 3 months from 19% to 40%. Assuming 15 months for enrollment and 12 months minimum follow-up, 40 evaluable patients (including expansion) will provide 97.5% power to reject 3 month PFS rate of 19% in favor of 3 month PFS rate of 40% using a one-sample survival test with one-sided 5% significance level using STPLAN (MD Anderson Biostatistics software) [6]. With estimated accrual of 1 patient every 2 months in the expansion cohort, we anticipate 18-24 months for patient enrollment followed by an additional year of follow up time. Expected time to study completion is 3 years from date open to enrollment.

For the secondary objectives utilizing patient samples, we anticipate that we will be able to obtain complete sets or measurements for all patients (pre-treatment, on-treatment, and post-treatment) to permit analysis of inpatient pharmacodynamic effect of therapy. However, a critical component of this study is the analysis for exploratory endpoints, which are hypothesis-generating in regards to potential biomarkers for response in sarcoma patients treated with concurrent axitinib/pembrolizumab. Thus, if our primary endpoint is met by the conclusion of enrollment and the combination appears active with potential benefit to patients, yet collection of tumor biopsies and peripheral blood sample collection was incomplete, we would consider extending enrollment to an additional 10 patients in an effort to obtain complete paired samples at the baseline, cycle 3, and off-study timepoints in responders and non-responders.

Power considerations for correlative studies: If we estimate 75% collection of complete, interpretable biopsies and blood samples from 40 patients, our analysis set of responders vs. non-responders will include approximately 10 responding patients and 20 non-responding patients. A sample size of 10 in the responder group and 20 in the non-responder group will provide 89.4% statistical power to detect a difference in mean change of 2.5 with a standard deviation of 1 at both time points, and a correlation between two measurement pairs of 0.2. The significance level is 0.00083 using Bonferroni adjustment ( $=0.05/60$ ).

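### Cycle 3 marker changes are tested against 3-month progression status in a sample that depends partly on that status, and the stated 89.4% power assumes collection unrelated to outcome

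*Combined protocol and SAP*

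**What the plan says.** Section 13.2.1 sets the condition for the on-treatment samples: "For patients who have successfully completed two cycles of axitinib/pembrolizumab therapy, the following on-treatment correlative studies will also be performed".

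Section 7.0 fixes the timing: "The first cycle of treatment will be seven weeks, with one week of axitinib alone prior to initiation of pembrolizumab", and then "Subsequently, six-week cycles of treatment consist of twice daily oral doses of axitinib administered continuously". Section 14.1 sets the response scans: "patients should be re-evaluated for response every 12 weeks (84 days, ±7 days) from date of Enrollment". Section 12.2.14 places the first of these before treatment at Cycle 3 Day 1, the visit at which the biopsy and blood are taken.

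Section 16.3 defines three marker changes: "Cycle 3 marker value minus Baseline marker value, Progression marker value minus Cycle 3 marker value, Progression marker value minus Baseline marker value". Each is tested against clinical benefit status and also "with progression-free status at 3 months (progression vs. no progression), we will use a Wilcoxon rank sum test". Changes in circulating tumor cell counts are tested against the same 3-month status.

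Section 11.0 lists among the reasons for which treatment may be discontinued: "The patient demonstrates radiologic progression by RECIST 1.1". DLT and adverse events that make continuation an unacceptable risk are also listed. An exception lets a patient with RECIST progression stay on if the investigator judges that there is clinical benefit.

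Section 16.4 assumes 75% complete sets from 40 patients, so that "our analysis set of responders vs. non-responders will include approximately 10 responding patients and 20 non-responding patients". It states 89.4% power for that split.

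**The concern.** In two of the three changes, one of the two values exists only if the patient is still being treated at about 3 months. Progression, death and toxicity before that date remove the value. Progression and death are also what make a patient a progressor in the test. Whether the marker is observed therefore depends in part on the outcome, and the progressors who contribute are those who lasted through two cycles. A difference between the groups, or the lack of one, could reflect that selection.

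Timing adds a second limit. The Cycle 3 sample is drawn at or just after the scan that decides 3-month status. An association found this way can describe what accompanies progression, but it cannot by itself show that the marker change predicts it.

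Section 16.4 calls the exploratory analyses a critical part of the study and attaches a Bonferroni-adjusted power figure to them. That figure applies one collection rate to everyone. I found no rule in Section 16.3 for missing Cycle 3 values.

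**Working it through.** **Timing.** Cycle 1 is 49 days and Cycle 2 is 42 days (Section 7.0). 49 + 42 = 91, so Cycle 3 Day 1 is day 92. Three months is 365.25/4 = 91.3 days. Sample and outcome coincide.

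**Who can be evaluable without a Cycle 3 sample.** The Section 16.2 analysis set needs 80% of scheduled axitinib, two pembrolizumab infusions and one post-baseline assessment. The infusions fall on days 8 and 29 (Section 8.0). A patient who has both, is assessed, and stops for progression or toxicity before day 91 can be evaluable and still have no Cycle 3 value. Section 1.5 reports one ASPS patient who progressed before 3-month imaging and one who had PD at 3 months and withdrew consent. It does not say whether either gave a sample.

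**The stated power.** Inputs from Section 16.4: difference in mean change 2.5, SD 1 at each time, correlation 0.2, alpha 0.05/60 = 0.00083, groups of 10 and 20.

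- SD of change = √(1 + 1 − 2 × 0.2) = √1.6 = 1.265
- Standardized difference = 2.5/1.265 = 1.976
- Noncentrality = 1.976/√(1/10 + 1/20) = 5.10, with 28 degrees of freedom
- Two-sided t-test power = **89.4%**

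This reproduces the plan. Sidedness is not stated there; a one-sided t-test gives 93.3% and does not match.

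**Where the 20 non-responders come from.** At the design 3-month PFS of 40%, 16 of 40 patients are progression-free and 24 have progressed. Ten complete responder sets at 75% imply 10/0.75 = 13.3 responders. If all of these are progression-free at 3 months (an assumption; Section 16.4 does not define a responder), 16 − 13.3 = 2.7 progression-free non-responders remain. They supply 2.0 complete sets at 75% collection and 2.7 at most. The other 17.3 to 18.0 sets must come from 3-month progressors, that is 72% to 75% of the 24.

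**Power if fewer non-responders are sampled.** Same t-test and alpha, 10 responders:

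| Non-responders with a Cycle 3 value | Power |
|---|---|
| 20 | 89.4% |
| 14 | 79.5% |
| 10 | 65.4% |
| 5 | 31.8% |

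The documents do not say which row applies.

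**The planned test.** Section 16.3 uses the Wilcoxon test for these changes. Simulated power of the exact two-sided test at 10 versus 20 is about 85% to 86%. At 10 versus 4 its smallest possible p-value is 2/1001 = 0.0020, above 0.00083.

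**The progression-status contrast.** Section 16.4 gives no power for it. With 75% of the 16 progression-free patients sampled (12), the same t-test calculation gives 92.3% if 75% of progressors are sampled (18), 81.1% at 50% (12) and 47.5% at 25% (6). These fractions are assumptions.

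**The case against.** Section 13.2.1 asks only for two completed cycles. It does not exclude a patient whose scan has just shown progression, and pre-dose is a statement about timing. The only scheduled scan before Cycle 3 falls close to the end of Cycle 2, so progression first seen there is found in patients who have completed, or nearly completed, the two cycles. The Section 11.0 exception keeps some progressors on treatment. If progressors were sampled at the plan's 75%, power for the progression-status contrast would be 92.3%, above the figure in Section 16.4. All of this stands, and the documents give no figure for the loss. Retention under the exception is itself selective, though, because it rests on judged benefit.

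The third change, off-study or progression minus baseline, needs no Cycle 3 value, and Section 3.3 requires only one post-treatment biopsy and blood draw for evaluability. That also stands; the other two changes are affected.

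The 10-versus-20 split is responders against non-responders, and non-responders include stable disease. This is correct. The link to progressors rests on the 40% planning rate and on responders being progression-free at 3 months.

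The two-infusion and post-baseline-assessment requirements remove many very early losses from the 40. They do not remove those between the second infusion and day 91. The 25% allowance and the possible 10-patient extension concern how many sets are missing, not whether missingness follows outcome.

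Finally, the analyses are labelled exploratory and test association. A marker measured alongside the outcome is acceptable for describing association or pharmacodynamic effect. That is a reason to keep the 3-month-status test, with its limits stated.

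**Conclusion.** The point holds in a limited form. Tests of Cycle 3 changes against 3-month status use a selected subset of progressors, with a marker measured as the outcome is read. The 89.4% is correctly calculated, but it is conditional on collection unrelated to outcome. At the plan's own 40% rate, and if all responders are progression-free at 3 months, it needs about 17 to 18 complete sets from 3-month progressors. Power drops just under 80% at 14 sampled non-responders and to about one third at 5.

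A reader might infer that progressors will have no Cycle 3 sample, so that the comparison disappears. The documents do not support this: patients found to have progressed on the roughly 12-week scan may still be sampled, some may stay on treatment, and no retention figure is given. Nor is 89.4% a claim about progressors versus progression-free patients; Section 16.4 makes none.

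The primary endpoint is not affected. The matter should be settled before biomarker results are reported, because otherwise an association in a selected group could be read as predictive and as well powered.

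**What to change.** In Section 16.3:

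- Add a landmark analysis of Cycle 3 changes against PFS counted from Cycle 3 Day 1, in patients progression-free at that visit. Make it the main analysis for any predictive claim.
- Keep the 3-month-status test of Cycle 3 changes as descriptive. Report how many patients in each outcome group have a Cycle 3 sample and why the others do not.
- Use 3-month status as the outcome for markers measured earlier: baseline, and Cycle 1 Day 8 in the expansion cohort.

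In Section 16.4, state that 89.4% assumes collection unrelated to outcome, and give power for 10 responders against a range of sampled non-responders: 20 (89%), 14 (80%), 10 (65%) and 5 (32%).

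The cost is a less favourable exploratory power statement and slightly more analysis. The landmark set leaves out patients who have progressed by that visit, which is why it is added to the 3-month-status test and does not replace it. No new samples or visits are needed.

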### 13.3 Off-Treatment Specimen Collection (End of Treatment or EOT visit)

The following must be performed at the EOT visit and should occur 30-days ( $\pm$  7 days) after the last dose of study treatment.

- 5 core biopsies (minimum of 2), 18-22 gauge in diameter and at least 1 cm in length, will be obtained. The interventional approach used to obtain the sample (ultrasound or CT guided biopsy) will be selected by the medical personnel performing the biopsy. If possible, the biopsy site should be in the same tumor initially biopsied prior to therapy.
  - One needle core biopsy will be transported in formalin to pathology for immunohistochemistry evaluation of immunologic markers. This analysis will be performed in collaboration with [name] at MD Anderson Cancer Center. Samples will be deidentified and sent to his laboratory for multiplex immunohistochemistry.
  - Unstained slides from the formalin fixed biopsies will be sent to Nanostring for RNA expression analysis using the Universal Immunooncology Expression Panel under a collaborative research agreement to identify potential biomarkers of response.
  - The remaining cores (if any) will be collected in cell culture media and transported to the [name] lab for preparation of a single cell suspension, isolation of lymphocytes, and immediate analysis by flow cytometry. For expansion patients, additional cores will be collected for RNA analysis and performance of T cell receptor sequencing and clonality assays using the Archer DX platform.
- Patients will also undergo phlebotomy for analysis of circulating mononuclear cells with banking of serum fractions for later analysis.
  - (6) 10 cc green top tubes and (1) 10 cc purple top tube will be collected for each time point. Samples will be separated using a Ficoll gradient. Mononuclear cells will be removed, washed, treated with RBC lysis

- process, then either stained immediately for flow cytometric analysis or frozen for later use. Aliquots of plasma will also be frozen. One tube of PBMCs will be preserved in RNA later for T cell clonality assays using the ArcherDX platform.
- Banked PBMCs will be sent out to Simpatica Medicine for RNA expression analysis to identify potential biomarkers of response under a collaborative research agreement.
  - Banked plasma samples will be analyzed for plasma angiogenic activity in collaboration with [name] at University of Miami. Samples will be exposed to human umbilical vein endothelial cells and angiogenic activity measured.
- Additional peripheral blood will be obtained for circulating tumor cell (CTC) analysis.
    - Two 10 cc Cell-Saver tubes will be drawn and transported immediately to the laboratory of [name] lab for analysis. Blood will be filtered and one slide stained for H&E to detect CTCs. The other slide will be reserved for additional analysis, including genomic analysis, FISH, or immunocytochemistry depending on the specific histology. The number of CTCs will be recorded for each patient.

